### 6.3. DOSE, ROUTE AND SCHEDULE OF IMP ADMINISTRATION

Ladarixin will be administered orally at the dose of 400 mg twice a day for 3 cycles of 14 days on / 14 days off. Placebo will be administered with the same treatment schedule. Administration will be extended up to 12 months (13 cycles) **only after additional chronic toxicity data support such longer treatment.**

The two daily doses will be administered at about 12hour interval (morning and evening; ideally between 6:30/11:30 and 18:30/23:30). At each administration, 2 capsules will be swallowed with a glass of water, at least 2 hours apart from breakfast or dinner.

### 6.4. CRITERIA FOR SCHEUDLE ADJUSTMENT/DOSE-MODIFICATION OR DISCONTINUATION OF THE IMP

#### 6.4.1. Criteria for schedule adjustment or dose modification

No schedule adjustment and/or dose modification is foreseen, except for discontinuation of IMP as detailed below.

#### 6.4.2. Criteria for discontinuation of the IMP

The IMP will be discontinued in the case:

- QTcF is either  $> 500$  msec or increases by  $> 60$  msec from screening measurement on two consecutive ECG readings taken 1 hour apart;
- The patient develops any significant cardiovascular disease/abnormality;
- The patient develops renal (calculated eGFR  $< 60$  mL/min) or hepatic (increased ALT/AST  $> 3 \times$  ULN and increased total bilirubin  $> 3$  mg/dL [ $> 51.3 \mu\text{mol/L}$ ]) dysfunction as well as hypoalbuminemia (serum albumin  $< 3$  g/dL);
- Pregnancy occurs (female patient);
- The patient develops any significant systemic infection that must be assessed on a case-by-case basis by the investigator regarding whether they are serious enough to warrant discontinuation.
- The patient develops ketoacidosis or hypoglycemic coma.

Occurrence of any condition that qualify the patient to treatment discontinuation will be specifically monitored through ECG readings and laboratory tests obtained at the visits scheduled at the end of the 3rd (Week 11), 6th (Week 23) and 9th (Week 35) treatment cycles.

In addition, the IMP will be immediately discontinued in the event of any other possibly drug related occurrences that the Investigator believes might compromise patient's safety.

If the IMP administration is prematurely discontinued, the primary reason for discontinuation must be recorded in the eCRF. Patients who discontinue the treatment with the IMP will NOT be withdrawn from the study by default, but will be asked to complete safety and efficacy observations as per the protocol, unless otherwise they withdraw their consent.

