### 2.3. PHARMACOKINETICS AND PRODUCT METABOLISM

The pharmacokinetics of DF2156Y was studied in rats and mice after single i.v. and oral administration and after multiple oral administrations in rats and dogs within the toxicity studies.

DF2156Y is almost completely absorbed after oral administration in rats with an absolute bioavailability higher than 90%. DF2156Y is slowly eliminated from plasma in all the three species tested ( $t_{1/2}$  ranging from 25 hours to 30 hours). Gender differences in pharmacokinetic profile after oral administration (slightly lower exposure in females than in males) were observed in rats but not in dogs.

A metabolite of DF2156Y named DF2108Y (R enantiomer) was identified, using a non-chiral analytical method, in both rats and dogs. On the basis of the chiral analytical determination, the S enantiomer (DF2227Y) was noted in the plasma of both rats and dogs. The *in vivo* interconversion of DF2108Y into DF2227Y was about 90% in rats.

In male and female rats DF2227Y was the major and long lasting circulating metabolite. After repeated daily oral administration of DF 2156A, this metabolite showed an accumulation ratio ranging between 1.4 and 2.4. After the daily oral administration of DF 2156A at 200 mg/kg for 6 weeks, the parent compound and the metabolites showed comparable exposure in Wistar and Sprague Dawley rats either at day 1 or after repeated administrations.

In humans, single oral doses of ladarixin (25 to 400 mg) provided quantifiable plasma concentration of DF2156Y within 1 hour, with peak concentration being reached between 1 and 3 hours. After single doses, DF 2156A was excreted mainly as unmodified in human urine. The presence of the two

metabolites found in animal species (DF 2108Y and DF 2227Y) was confirmed in humans. Dose proportionality over the entire dose range investigated was observed as well as  $t_{1/2}$  (11-19 h) remained constant across the range of doses evaluated. Renal clearance accounted for approximately 60-80% of the total clearance of DF 2156Y. The dose proportionality for the main PK parameters was also seen for the two metabolites (DF 2108Y and DF 2227Y).

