### 6.2. IMP DISPENSATION

The IMP will be dispensed quarterly only by the Pharmacist (or authorized designee at site).

The IMP will be dispensed via IRS as Patient Kits during the Randomization Visit and then during the Visits scheduled at the end of the 3rd (Week 11), 6th (Week 23) and 9th (Week 35) treatment cycles, after check of inclusion/exclusion criteria (at Randomization) and discontinuation criteria at the scheduled visits \* (see [Section 6.4.2](#)).

A total number of 13 Patient IMP Kits will be dispensed to each randomized subject as follows:

- at Randomization Visit dispensed 3 Patient Kits for the Cycles 1, 2 and 3
- at Week 11 Visit dispensed 3 Patient Kits for the Cycles 4, 5 and 6
- at Week 23 Visit dispensed 3 Patient Kits for the Cycles 7, 8 and 9
- at Week 35 Visit dispensed 4 Patient Kits for the Cycles 10, 11, 12 and 13

[\* Results of ALT/AST, bilirubin, creatinine, albumin, ECG readings and pregnancy results should be made available by local laboratory in time to allow Patient Kits dispensation as soon as possible during the visit. If this expedite timing cannot be achieved, Patient Kits might be delivered to patient named address by a selected courier (CRO to support shipment). Study drug dispensation will be performed as soon as possible after check of discontinuation criteria.]

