#### 6.5. ACCOUNTABILITY OF THE IMP

All supplies will be maintained under adequate security by the designated member of site staff, until they are dispensed to the patients. The Investigator will ensure that study treatment is only dispensed by designated staff within the center.

When the IMP is received at the site, designated member of site staff will check for accurate delivery and acknowledge receipt by signing and dating the documentation provided by or on behalf of Dompé and returning it to Dompé or to the appointed CRO. A copy will be retained for the Investigator/Pharmacy file.

The dispensing of the IMP will be carefully recorded on the eCRF and appropriate drug accountability forms and an accurate accounting will be available for verification by the CRA at each monitoring visit. Immediately before dispensing each Patient Kit, the kit label will be completed with the required information (i.e. Patient ID number and Investigator Name).

Drug accountability records will include:

1. the confirmation of receipt of the IMP at the trial site,
2. the dispensing of the IMP to the patient,
3. the receipt of IMP returned from the patient,
4. the disposition of unused product(s),
5. accounts of any IMP accidentally or deliberately destroyed,

They should include dates, quantities, batch numbers, expiration dates (if applicable), and any unique code numbers assigned to the IMP and/or patients. Investigators should maintain records which document adequately that:

1. the patients were provided the doses specified by the protocol/amendment(s),
2. the IMP provided was fully reconciled at the site.

The administration of the IMP (date/time for each administration) will be recorded by the patient in the Patient Diary whose data will be checked by the Investigator during the next study visit.

The CRA will review the drug accountability forms/eCRF and check all IMP (both unused and used) prior to making arrangements for their disposal.

IMP which has been dispensed to a patient and returned unused will not be re-dispensed to a different patient. Unused IMP (capsules) must remain in the blisters within the Patient Kit and must not be discarded or used for any purpose. Any remaining test material at the end of the trial will be returned to Dompé or disposed of, as determined by Dompé.

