After having confirmed the patient has not developed a condition that prevents his/her continuing participation into the study\*, he/she will be provided with the Patient Kits matching his/her randomization number, together with the Patient Diary, according to the schedule reported below: (see also section 6.2).

- at Week 11 Visit dispensed 3 Patient Kits for the Cycles 4, 5 and 6
- at Week 23 Visit dispensed 3 Patient Kits for the Cycles 7, 8 and 9
- at Week 35 Visit dispensed 4 Patient Kits of IMP for the Cycles 10, 11, 12 and 13

\* Results of ALT/AST, bilirubin, creatinine, albumin, ECG readings and pregnancy results should be made available by local laboratory in time to allow dispensation of Patient Kits as soon as possible during the visit. If this expedite timing cannot be achieved, Patient Kits might be delivered to patient named address by a selected courier (CRO to support shipment).

The administration of the IMP (date/time for each administration, number of capsules) will be recorded by the patient in the Patient Diary which data will be checked by the Investigator during the next study visit.

It is the responsibility of the Investigator (or designee) to check the information the patient will insert in the Patient Diary to ensure correct intake of the IMP. The Investigator will remind, and make sure patient still fully understands any appropriate treatment related information.

The Patient Kits containing all the blisters, either unused or empty, will be returned to and checked by the Investigator during the next study visit.

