### 7.4.1. Additional visits during treatment

During treatment, patient will attend the center for study assessments on 2 additional visits at Month 6 (Week 26) and Month 12 (Week 52). At least 10 days before each scheduled visit, the CGM sensor will be placed.

During these visits the following will be assessed:

- Waist and waist/hip circumference and calculation of eGDR.
- Patient Diary check (information other than IMP administration at Month 6, any information at Month 12).
- Insulin requirement (IU/kg/day averaged over the previous 3 days).
- Number of self-reported episodes of severe hypoglycemia in the interval.
- Blood sampling for measurement (centralized laboratory) of HbA1c.
- MMTT. Blood samples for measurement (centralized laboratory) of C-peptide and glucose will be drawn pre-meal (2 basal samples in the range between -20 to 0) and 15, 30, 60, 90, 120 min after the meal.
- Blood sampling for measurement (centralized laboratory) of CCI [REDACTED]  
[REDACTED].
- CGM sensor download for evaluation of Glucose Variability Indices from CGM.
- Blood sampling for measurement (local laboratories) of "Safety Laboratory Tests" (Month 12 only).
- Vital signs (Month 12 only).

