## 14.2. APPENDIX 14.2 – STUDY FLOW CHART

100 days (run-in phase)

1st insulin first IMP dose

Procedures	Screening	Baseline (within 3 weeks to C1 start)	Randomization (within 3 days of C1)	TREATMENT PERIOD (cycle = C) - 13 Cycles (C1 - C13)								FOLLOW- UP	
				C1 - C3	Week 11 (end of 3 rd cycle)	C4 - C6	Week 23 (end of 6 th cycle)	C7 - C9	Month 6 Week 26±2 Visit while on C7	Week 35 (end of 9 th cycle)	C10 - C13	Month 12 Week 52±2	
Tests to be performed at a centralized laboratory													
Test to be performed at the local laboratory													
Informed Consent Form	X												
Eligibility criteria Randomization	X	X	X										
Auto-antibodies  & Fasting C-Peptide 	X												
Medical history	X												
BP/HR		X			X		X			X		X	X
weight, height, waist & waist/hip circumference	X								X			X	X
eGDR	X								X			X	X
Insulin requirement previous 3 days	X								X			X	X
Self Reported Severe Hypoglycemia	X								X			X	X
HLA DR-DQ haplotypes, Proinsulin	X												
HbA1c, CCG		X							X			X	X
Safety Laboratory Test (hematology & biochemistry) 	X				X		X			X		X	X
MMTT 	X								X			X	X
Pregnancy Test	X				X		X			X			
12 lead ECG	X				X 		X 			X 			
CGM download 	X 								X 			X 	X 
IMP dispensation 			X		X		X			X			
Patient Diary delivery/check			X		X		X			X		X	X
Check discontinuation criteria 					X		X			X			
Patient Phone call 				X	X	X	X	X	X	X	X	X	X
AE/SAE recording	X												X
Prior and Concomitant Medication	X												X

 anti-GAD; IAA (if obtained within 10 days of the onset of insulin therapy); IA-2; ZnT8. fasting C-peptide must be  $\geq 0.205$  nmol/L on two occasions. tests performed at Baseline should be planned to ensure the samples are sent to the laboratory and results are available in time for randomization.

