# PPD

*the morning. This may happen, but conventionally days and not day periods (morning / evening) will be considered. For these cases is possible that intake may last 15 days instead of 14.*

In case the kit was dispensed, it was returned, and the number of capsules taken is 0 (therefore we cannot define the start cycle date and end cycle date), we will follow the following convention:

- Start Cycle x date will be as scheduled date: start cycle x-1 date (previous cycle) +28 days
- End Cycle x date will be equal to start cycle x date
- On period will be set to 0 days

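### The scheduled ECGs that check the QTcF stopping criterion nominally fall 1–7 days after a cycle's last dose, so the check is poorly timed, though not blind, for on-drug prolongation

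*Protocol*

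**What the plan says.** Protocol 6.4.2 stops the drug if QTcF exceeds 500 msec, or rises by more than 60 msec from screening, on two readings an hour apart. It says that the stopping conditions are "specifically monitored through ECG readings and laboratory tests obtained at the visits scheduled at the end of the" third (Week 11), sixth (Week 23) and ninth (Week 35) cycles.

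Sections 6.2 and 7.3 make the same visits the condition for dispensing. Three kits are released at each of Weeks 11 and 23. The last release is "at Week 35 Visit dispensed 4 Patient Kits for the Cycles 10, 11, 12 and 13".

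The flow chart (Appendix 14.2) labels another visit "Month 6 Week 26±2 Visit while on C7", but the Month 6 assessments in 7.4.1 include no ECG. None is listed at Month 12 (7.4.1) or Month 18 (7.4.2) either.

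Section 2.5.1 gives a half-life of 11 to 18 h and treats the drug as cleared after about 98 h. SAP 8.4 summarises QTcF and its change from baseline by visit, without reference to dosing time.

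**The concern.** Protocol 2.4.3 names QT prolongation as the cardiovascular risk suggested by the animal work. In the dog studies (2.2) the effect had resolved by the end of recovery, so a reading taken off drug can look normal when an on-drug reading would not.

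Each cycle is 14 days on drug followed by 14 days off. A visit at the end of a cycle can therefore come after much or nearly all of the parent drug has gone. If QTcF follows parent concentration, a rise that meets the stopping criterion during dosing could be absent at the visit, and kits for the next three or four cycles would be released. By-visit QTcF tables would also pool readings taken near a dose with readings taken after washout.

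**Working it through.** **Inputs.** Day 1 is the first dose (Protocol 7.2). There are 13 cycles of 28 days, 14 on then 14 off (SAP 6.1). The ECG visits are Weeks 11, 23 and 35 (Protocol 6.4.2). Visit windows are given only for Months 6, 12 and 18 (Protocol 7). The half-life is 11–18 h and clearance takes about 98 h (Protocol 2.5.1).

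**Assumptions.** Week w covers days 7w−6 to 7w. Parent drug decays exponentially from its last-dose level.

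**The plan's own figure.** 98/24 = 4.1 days. 98/18 = 5.4 half-lives, leaving 2.3%. 98/11 = 8.9 half-lives, leaving 0.2%. The stated four days is consistent with a rule of five or more half-lives.

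**Calendar.** Cycle k is dosed on days 28(k−1)+1 to 28(k−1)+14, and the next cycle starts on day 28k+1.

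| Cycle | Dosing days | ECG visit | Visit days | Days after last dosing day | Next cycle starts |
|---|---|---|---|---|---|
| 3 | 57–70 | Week 11 | 71–77 | 1–7 | 85 |
| 6 | 141–154 | Week 23 | 155–161 | 1–7 | 169 |
| 9 | 225–238 | Week 35 | 239–245 | 1–7 | 253 |

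If Week w means day 7w+1, the visits fall on days 78, 162 and 246, which is 8 days after the last dosing day. The first convention fits the flow chart better. It puts Week 26 on days 176–182, inside cycle 7 dosing (days 169–182). The elapsed convention gives day 183, the first off day.

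**Parent drug remaining**, 2^(−t/half-life):

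| Time since last dose | 11 h | 18 h |
|---|---|---|
| 2 h | 88.2% | 92.6% |
| 6 h | 68.5% | 79.4% |
| 12 h | 46.9% | 63.0% |
| 24 h | 22.0% | 39.7% |
| 48 h | 4.9% | 15.7% |
| 96 h | 0.24% | 2.48% |
| 168 h | 0.003% | 0.155% |

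**What keeps the check from being blind.** A morning visit on the first day of the visit week, after an evening last dose, sits near the 12 h row. SAP 6.1.2.2 also covers a first intake in the evening and a last intake in the morning: "For these cases is possible that intake may last 15 days instead of 14". The final dose of cycle 3 can then fall on the morning of day 71, which is already in Week 11, and a visit that day would sit near the 2–6 h rows.

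**Dosing released per check.** 3 × 14 = 42 days after Weeks 11 and 23. 4 × 14 = 56 days after Week 35.

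**Could a later visit close the gap?** Cycle 13 dosing ends on day 350 and Week 52 is days 358–364. An ECG at Month 12 would nominally be 8–14 days after the last dose, even if one were scheduled.

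**The case against.** The strongest reply is that QT has already been examined where it counts. Protocol 2.4.3 reports that core-laboratory review of the phase 1 ECGs, including the relationship between concentration and QTcF, found no clinically significant effect on repolarization. Phase 1 repeated dosing reached 400 mg b.i.d., and steady state came around Day 5 to 6 (2.3). After 120 h of dosing, parent drug is at 1 − 2^(−120/18) = 99.0% of steady state or higher, so days 7–14 of a cycle add under 1%. Fifty patients with type 1 diabetes then took the same dose for three cycles without a safety concern being raised. On this view the local ECGs are a backstop for dispensing, and QTcF is not a listed safety endpoint (Protocol 4.3, SAP 3.7).

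Other protections also apply. QTcF above 470 msec is excluded at entry (5.2). The investigator can stop the drug for any cardiovascular abnormality or possibly drug-related event (6.4.2). Patients are contacted at least every 2 to 3 weeks (7.1.1). Nothing bars an unscheduled ECG.

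Most of this stands, and it makes the clinical weight low. Two limits remain. The phase 1 volunteers were all male, while QT prolongation in the 3-month dog study tended to be stronger in females and this trial enrols women. The earlier diabetes trial included women, but the protocol shows no ECG results from it.

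A reader might infer that the report would hide the timing. It would not: SAP 4.1 lists all collected and derived data and SAP 6.1.5 lists accountability and compliance detail by cycle, so the lag can be worked out by hand. What is missing is the derived interval and any summary that uses it.

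**Conclusion.** The point holds as a timing weakness of low priority. The scheduled QTcF check nominally falls 1–7 days after the last dosing day (8 on the elapsed-week reading). Parent drug is then at about 22–40% of its last-dose level at 24 h and at most 2.5% by 96 h. A rise related to parent concentration could be missed at the check that releases the next 42 or 56 dosing days.

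This rests on the nominal calendar, exponential decay, and an effect that follows parent drug.

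Two stronger readings are tempting and unsupported:

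- **That the stopping criterion cannot detect on-drug prolongation, or that patients were left unprotected.** With no window stated and a possible 15th dosing day, some visits can fall within hours of a dose. The phase 1 findings and the other safeguards also count against it.
- **That later readings say nothing about on-treatment QT.** Protocol 2.3 confirms two metabolites in humans and describes one as long-lasting in rats, but no human half-life is given for either. A metabolite-driven effect might still be visible days after dosing.

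**What to change.** **1. SAP 8.4.** Derive time since last IMP intake for each ECG, show it in the ECG listing, and describe QTcF change from baseline by that time, for example within 1 day of the last dose versus later. State only that the later readings were taken after most parent drug had cleared and give limited information on QT at on-drug parent exposure.

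The inputs exist. Protocol 7 records the date and time of every assessment, SAP 6.1.2.2 uses the last intake date in each cycle, and Protocol 6.5 says "The administration of the IMP (date/time for each administration) will be recorded by the patient in the Patient Diary". The cost is one derived variable and one listing column. Enrolment stopped early (SAP 1), so groups will be small, and the within-1-day group still mixes near-peak readings with readings at 22–40% of the last-dose level. The listing carries most of the value.

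**2. Any further dosing under this schedule.** Book the existing safety visit on the last dosing days of cycles 3, 6 and 9 (about days 69–70, 153–154 and 237–238). Take the ECG at a recorded time 1–2 h after the morning dose. Protocol 2.3 describes single doses "with peak concentration being reached between 1 and 3 hours", so a first reading at 1–2 h leaves room for the one-hour repeat within the peak. No visit or procedure is added, and results are still available before the next cycle.

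The downsides are:

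- The visit window is tighter.
- Laboratory and pregnancy tests fall 15–16 days before the next cycle (85 − 70 to 85 − 69) instead of 8–14 (85 − 77 to 85 − 71).
- After the morning dose, 2–6 of the cycle's 56 capsules remain (4–8 after an evening start). That kit "will be returned to and checked by the Investigator during the next study visit", and the last intakes are also checked later. Month 6 diary review excludes IMP intake, so cycle 6 would wait until Week 35.

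Because enrolment was stopped in March 2022, this second part probably comes too late for the present trial.

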#### 6.5. ACCOUNTABILITY OF THE IMP

All supplies will be maintained under adequate security by the designated member of site staff, until they are dispensed to the patients. The Investigator will ensure that study treatment is only dispensed by designated staff within the center.

When the IMP is received at the site, designated member of site staff will check for accurate delivery and acknowledge receipt by signing and dating the documentation provided by or on behalf of Dompé and returning it to Dompé or to the appointed CRO. A copy will be retained for the Investigator/Pharmacy file.

The dispensing of the IMP will be carefully recorded on the eCRF and appropriate drug accountability forms and an accurate accounting will be available for verification by the CRA at each monitoring visit. Immediately before dispensing each Patient Kit, the kit label will be completed with the required information (i.e. Patient ID number and Investigator Name).

Drug accountability records will include:

1. the confirmation of receipt of the IMP at the trial site,
2. the dispensing of the IMP to the patient,
3. the receipt of IMP returned from the patient,
4. the disposition of unused product(s),
5. accounts of any IMP accidentally or deliberately destroyed,

They should include dates, quantities, batch numbers, expiration dates (if applicable), and any unique code numbers assigned to the IMP and/or patients. Investigators should maintain records which document adequately that:

1. the patients were provided the doses specified by the protocol/amendment(s),
2. the IMP provided was fully reconciled at the site.

The administration of the IMP (date/time for each administration) will be recorded by the patient in the Patient Diary whose data will be checked by the Investigator during the next study visit.

The CRA will review the drug accountability forms/eCRF and check all IMP (both unused and used) prior to making arrangements for their disposal.

IMP which has been dispensed to a patient and returned unused will not be re-dispensed to a different patient. Unused IMP (capsules) must remain in the blisters within the Patient Kit and must not be discarded or used for any purpose. Any remaining test material at the end of the trial will be returned to Dompé or disposed of, as determined by Dompé.

